10.0 Data and Specimen Banking

10.1 Storage of specimens.

Muscle specimens and blood specimens for long-term storage will be stored in a freezer belonging to [name] research program at Northwestern University, in the freezer farm in the basement of Olson Pavilion. Specimens will be stored for up to 70 years, after which they will be destroyed.

10.2 Data to be stored or associated with each specimen.

PROTOCOL TITLE: Telmisartan Plus Exercise to Improve Functioning in PAD: The TELEX Trial

Specimens will be coded; meaning that a key will exist that can link the codes back to the direct subject identifiers. Each participant will be assigned a unique study ID number that can be traced back to the study participant. The muscle specimens and the blood samples that are stored will be labeled with this unique identifier and the date and time of the blood collection.

10.3 Procedures to release data or specimens.

Only [name] has control over release of study data or specimens. Any investigators seeking to analyze blood or muscle specimens must contact [name] for permission. Each request, if it occurs, will be considered on a case-by-case basis. [name] will obtain IRB approval prior to releasing any blood or muscle specimens for analysis, other than those tests specifically named in this application.

11.0 Data and Specimen Management

11.1 Data management.

We will use REDCAP for data entry, via NUCATS.

11.2 Power Estimates/Calculations.

On October 31, 2019 investigators along with the DSMB and the study sponsor, NHLBI, agreed to change the primary aim to a single comparison of telmisartan (with and without supervised exercise) vs. placebo (with and without supervised exercise) due to difficulty recruiting participants for the trial who were not already taking an ACE inhibitor or an angiotensin receptor blocker. Although the investigators will still aim to recruit as many participants as possible (up to the originally proposed sample size), this change in primary aim provides statistical power for a sample size of 112 participants. Power calculations still take into account an anticipated 10% drop-out rate at 6-month follow-up, i.e., we expect to have approximately 25 participants per group (i.e. 100 overall) completing the 6-month follow-up.

PAD participants will be randomized to one of four study groups:

Group A: telmisartan + supervised exercise therapy;

Group B: telmisartan + a “no exercise” control group;

Group C: placebo + supervised exercise therapy; and

Group D: placebo + a “no exercise” control group.

For our revised Primary Aim, we will determine whether Group A+B improves six-minute walk performance at 6-month follow-up, compared to Group C+D, stratified by the exercise status. 50 PAD participants in each group provides 80% power to detect a minimum difference of 0.566 standard deviations (SD) between Groups A+B and C+D in changes of six-minute walk performance, using a two-sided two-sample t-test with a significance level of 0.05. As a sensitivity analysis, the following table summarizes the power for testing the primary aim with different total numbers of enrolled participants.

PROTOCOL TITLE: **Telmisartan Plus Exercise to Improve Functioning in PAD: The TELEX Trial**

#total patients	112	116	120	128
Power for detecting 0.566 SD	80%	82%	83%	85%

In our SILC and GOALS trials (43,60), the observed differences in change of six-minute walk performance at 6-month follow-up between the intervention and control groups were 0.70 SD and 0.78 SD, respectively. In our SILC and GOALS trials, these observed differences represented a difference in six-minute walk change of 40 meters between the intervention and control groups (43,60), a clinically meaningful difference (79). Thus, we have adequate power for detecting similar or slightly smaller difference in the Primary Aim.

For Secondary Aim 1, we will determine whether Group A achieves greater improvement in six-minute walk at 6-month follow-up, compared to Group B and Group C, respectively. 25 participants in each group provides 70% power to detect a minimum difference of 0.72 SD between Groups A and B and between Groups A and C, respectively, in change of six-minute walk performance, using a two-sided two-sample t-test with a significance level of 0.05. For our Secondary Aim 2, we will determine whether Group B improves maximal treadmill walking, the WIQ, and the SF-36 PF score at 6-month follow-up, compared to Group D. The 25 PAD participants in each group also provide 70% power to detect a minimum difference of 0.72 SD.

For our Secondary Aim 3, we will determine whether Groups A+B combined improves maximal treadmill walking distance, the WIQ, and the SF-36 functioning score, compared to Group C+D combined, stratified by exercise status. 50 PAD participants in each group provides 80% power to detect a minimum difference of 0.566 SD between Groups A+B and C+D using a two-sided two-sample t-test with a significance level of 0.05. Thus, we have adequate power to detect effect sizes similar to the effect size in 6-minute walk distance in SILC and GOALS for all three Secondary Aims.

For Tertiary Specific Aim 1, we will determine whether Group B achieves greater improvement in maximal treadmill walking distance, the WIQ, and the SF-36 functioning score, compared to Group D. For Tertiary Specific Aim 2, we will determine whether Group A achieves greater improvement in maximal treadmill walking distance, the WIQ, and the SF-36 functioning score, compared to Group B and Group C, respectively. 25 participants in each group provides 60% power to detect a minimum difference of 0.64 SD between Groups A and B and between Groups A and C, respectively, using a two-sided two-sample t-test with a significance level of 0.05.

In our SILC trial (43), the observed differences in change of maximal treadmill walking distance, WIQ distance score, and SF-36 functioning score were 0.60 SD, 0.59 SD, and 0.61 SD, respectively. Thus, we should

PROTOCOL TITLE: Telmisartan Plus Exercise to Improve Functioning in PAD: The TELEX Trial

have reasonable power to detect similar effect sizes for outcomes in our Tertiary Aims.

Statistical Analyses. Analyses will be performed according to the intention to treat principle. Data will be analyzed according to each participant's originally assigned group, irrespective of whether the participant adheres to the assigned group. For the Primary Aim, we will use analysis of covariance (ANCOVA) to compare changes in six-minute walk performance at 6-month follow-up between Group A+B combined and Group C+D combined, adjusting for study site (Northwestern or Tulane) and randomization to exercise status. For our Secondary Aim 1 and our Secondary Aim 2, we will use two sample two-tailed t-tests to compare changes in six-minute walk at 6-month follow-up between Groups A and B, between Groups A and C, and between Groups B and D, all stratified by study site. For our Secondary Aim 3, we will use ANCOVA to compare changes in maximal treadmill walking distance, the WIQ, and the SF-36 physical functioning score between Groups A + B vs. Groups C + D, adjusting for study site and randomization to exercise. For our Tertiary Specific Aim 1, we will use t-tests to compare maximal treadmill walking distance, the WIQ, and the SF-36 functioning score, between Groups B and D stratified by study site. For our Tertiary Specific Aim 2, we will use t-tests to compare maximal treadmill walking distance, the WIQ, and the SF-36 physical functioning score, between Groups A and B, and between Groups A and C, respectively, also stratified by study site. For our Exploratory Aims, we will use ANCOVA to compare changes in gastrocnemius muscle biopsy measures of each muscle measure between Groups A+B vs. C+D adjusting for study site and randomization to exercise. We will also compare Groups A, B, and C, respectively vs. Group D using two sample t-test stratified by study site. When the distribution of changes in the primary, secondary, and exploratory outcomes of interest is "very non-Gaussian", we will either apply appropriate transformation before conducting t-tests or perform Wilcoxon rank-sum test for the comparisons. Prior to analyses, we will also check the potential imbalance of socio-demographic factors and prognostic factors (such as age, sex, race, baseline outcome measure, ABI, BMI, smoking status, comorbidities, and relevant medication use) between the two groups using t-tests for continuous factors and chi-square test for discrete factors. If there is any indication of major imbalance in these factors or baseline variables are associated with the change in outcome of interest, we will perform ANCOVA to further adjust for the relevant baseline factors as potential confounders, in addition to randomization to exercise status and site, for two-group comparison. Similar analysis will be performed for exploratory aims. In the analysis for the secondary, tertiary and exploratory aims, we will not adjust for multiple testing. However, we will report all the results regardless of their significance to present an overall picture of the treatment effect of

PROTOCOL TITLE: Telmisartan Plus Exercise to Improve Functioning in PAD: The TELEX Trial

telmisartan. In additional exploratory analyses, adjustment for multiple comparisons may be performed.

Analyses regarding missing data: If missing data due to participant dropout is missing completely at random, then the aforementioned analyses based on available data provide valid statistical inferences. When missing data due to dropout is not missing completely at random, we will perform several sensitivity analyses. Specifically, we will employ the multiple imputation approach to account for missing data at 6-month follow-up under the assumption of missing at random (91). We will perform additional sensitivity analyses to guard against the possibility of missing not at random using extreme value imputation, selection models and shared-parameter models (92).

11.3 Steps to secure data to maintain confidentiality during storage, use, and transmission.

First, all research assistants must complete training in protection of subject privacy and prevention of disclosure of identifying information.

Second, all data collection forms are maintained in a secure office space.

Third, our study databases are maintained in locked computer files or on secure hard-drives that are password protected; to which only authorized staff have access. [name] or a study manager must provide permission for programmers and research assistants to access study databases.

Fourth, a study identification number will be assigned to each participant. This identification number will be used to label blood specimens, for example. In addition, most pages of our data collection forms will have only the study identification number listed (and not the participant's name, for example).

11.4 Quality Control.

Health interviewers will be trained by a senior coordinator and certified by [name] in each data collection element, using a detailed checklist. Health interviewers are rigorously evaluated for adherence to protocol, delineated in our manuals, prior to beginning data collection. They are re-certified approximately every six months by a project manager or [name]. When deficiencies are identified, interviewers undergo additional training and re-assessment. Ten percent of participants are randomly identified for quality control. This subset has their ABI measured twice by

PROTOCOL TITLE: Telmisartan Plus Exercise to Improve Functioning in PAD: The TELEX Trial

independent examiners and may have a split sample of muscle tissue (i.e. two samples from the same participant) sent for analyses. The second muscle sample is designated an arbitrary identification number to which the technician is blinded. Thus, quality control is monitored continuously. [name] meets with the exercise physiologist(s) to review individual participant's progress.

Blinding for data collection. The health interviewer collecting outcome data will be blinded to the study group assignment. Participants are instructed not to reveal their group assignment. If a participant reveals their group assignment, data collection is immediately stopped and another certified health interviewer is paged or contacted by telephone to continue the visit.

Missing Data. Missing data may occur when some participants are lost to follow-up. First, we will make every effort to ensure that participants return for 6-month follow-up. We will use proxies to help us locate participants we are unable to reach and we will mail letters to participants who do not respond to our telephone contacts. We will encourage participants who do not adhere to their assigned groups to return for six-month follow-up. We will provide transportation and monetary incentives. Thus, we anticipate that most participants will complete six-month follow-up data collection. Second, we will record the reason for dropout for each participant. If dropout is completely at random, then the aforementioned analyses based on available data provide valid statistical inferences. When dropout is not completely at random, we will perform several sensitivity analyses. Specifically, we will employ the multiple imputation approach to account for missing data at 6-month follow-up under the assumption of missing at random (91). We will perform additional sensitivity analyses to guard against the possibility of missing not at random using extreme value imputation, selection models and shared-parameter models (92).

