8.0 Study Endpoints

The primary study endpoint is the six-month change in the six minute walk data.

Secondary study endpoints include a) six-month change in treadmill walking performance; b) six-month change in Walking Impairment Questionnaire; c) six-month change in health-related quality of life, measured with the Short-Form-36 Physical Functioning Score.

Exploratory study endpoints are change in calf muscle biopsy measures, consisting of calf muscle biopsy-obtained satellite cell number, Type I muscle fiber composition, PPAR δ , PGC-1 α , AMPK quantity and activity, and relative gene expression of PPAR δ , PGC-1 α , AMPK, FOXO3A, and SIRT-1.

Additional exploratory outcomes are a) six-month change in usual-paced four-meter walking velocity; b) six-month change in fast-paced four meter walking velocity; c) six-month change in the short physical performance battery (SPPB) score.

All data will be collected at baseline and at the 6-month follow-up visit.

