Other measures related to skeletal muscle quality and function and related to fat measures of inflammation and senescence may also be performed at Northwestern, the University of Florida, and/or the University of Kentucky, Mayo Clinic or at other institutions as designated by the Principal Investigator.

PROTOCOL TITLE: Telmisartan Plus Exercise to Improve Functioning in PAD: The TELEX Trial

Medications. Participants and their physicians will be asked not to change their medications during the study if possible. Participants will be asked to bring all of their medications to baseline and follow-up visits and to monthly blood pressure check visits. We will systematically record names and doses of medications and inquire about medication changes at each of these visits. If we find differences in the use of specific medications between study groups (such as statins or cilostazol), we will adjust for these differences.

Other measures. Body mass index (BMI) will be assessed at baseline and follow-up by objectively measuring height and weight. Patient report will be used to document comorbidities. A four-meter walk test will be administered at usual and fastest pace at the baseline and follow-up visits. Participants will be asked to perform the usual paced four-meter walk at usual pace and the “fast paced” four meter walk at their fastest pace. Each of these short walks will be performed twice. Participants will be asked to complete a series of standing balance exercises and chair stands. Participants will undergo a physical exam by a physician and will have the blood pressure in their arm checked. Participants may be asked to return for a second blood pressure measurement at the discretion of the investigator (e.g. if the sitting blood pressure is not consistent with their typical blood pressure or if changes in medical condition or treatment may have spuriously altered the blood pressure value).

9.3 Overview of protection against risks.

Adequacy of protection against risks and methods to minimize potential risks. [name] and the study safety officers are responsible for overseeing results of monthly blood pressure checks and regularly scheduled potassium levels and measures of renal function and will follow up with the participant and/or their physician as necessary.

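### Baseline six-minute walk should be a fixed covariate in the primary ANCOVA: a small gain in precision from data already collected

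*Combined protocol and SAP*

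**What the plan says.** Section 11.2, Statistical Analyses, introduces the primary model with "For the Primary Aim, we will use analysis of covariance (ANCOVA) to compare changes in six-minute walk performance at 6-month follow-up", comparing all telmisartan with all placebo participants, "adjusting for study site (Northwestern or Tulane) and randomization to exercise status". Those are its only named covariates. Secondary Aim 3 uses the same model for treadmill distance, the WIQ and the SF-36 physical functioning score.

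The baseline outcome appears later in the same paragraph, as one item in an open list. The analysts will "check the potential imbalance of socio-demographic factors and prognostic factors (such as age, sex, race, baseline outcome measure, ABI, BMI" and others, by t-tests and chi-square tests. The consequence is conditional: "If there is any indication of major imbalance in these factors or baseline variables are associated with the change in outcome of interest", then "we will perform ANCOVA to further adjust for the relevant baseline factors as potential confounders, in addition to randomization to exercise status and site". No cut-off is given for either trigger, and the text does not say whether the further-adjusted result supports the named one or replaces it.

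Section 9.2, Medications, has a separate rule: "If we find differences in the use of specific medications between study groups (such as statins or cilostazol), we will adjust for these differences". It too has no cut-off.

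Baseline walk is available at no extra effort. Section 8.0 says of the endpoints: "All data will be collected at baseline and at the 6-month follow-up visit".

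**The concern.** When the outcome is a change score, its baseline value is usually the strongest covariate at hand, because baseline and change are negatively correlated through regression to the mean. Leaving it out of the named model gives up precision that the trial has already paid for. That matters somewhat more here because the target fell from 240 to 112 participants (section 1.1), and the plan sits at 80% power with little to spare.

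The secondary issue is clarity. If baseline walk is associated with change, the screen will usually fire, and the analysts will then hold two results for one primary comparison. One sentence would say which of them answers the primary aim.

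**Working it through.** **Inputs from section 11.2.** 50 completers per arm, difference 0.566 SD of change, two-sided alpha 0.05, stated power 80%, 10% drop-out. In the two earlier exercise trials, 40 m corresponded to 0.70 and 0.78 SD.

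**Assumed.** Correlation rho between baseline and six-month walk of 0.7 / 0.8 / 0.9, and equal variances at the two visits. The documents give neither.

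**Step 1: reproduce the plan's figure.** The noncentrality is 0.566 × √(50/2) = 2.83. With 98 df the noncentral t gives 80.0%. The power table also reproduces. Taking 90% of each total, halved, 112 / 116 / 120 / 128 give 80.3 / 81.7 / 83.0 / 85.4%, against 80 / 82 / 83 / 85% stated.

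**Step 2: variance removed by baseline.** For a common variance σ², the variance of change is 2(1 − rho)σ². The residual variance given baseline is (1 − rho²)σ². The ratio is (1 + rho)/2 = 0.85 / 0.90 / 0.95.

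**Step 3: power with baseline fixed.** Divide 2.83 by the square root of that ratio and use 95 df (100 observations, five parameters).

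| rho | Covariates perfectly balanced | Allowing for chance imbalance |
|---|---|---|
| 0.7 | 86.0% | 85.3% |
| 0.8 | 84.0% | 83.2% |
| 0.9 | 82.0% | 81.2% |

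The last column multiplies the noncentrality by √(1 − 2/99), for site and baseline walk. The same allowance for site alone, √(1 − 1/99) with 96 df, puts the named model at 79.6%. The gain is therefore 5.7 / 3.6 / 1.6 points. Under perfect balance, the difference detectable with 80% power falls from 0.566 SD to 0.522 / 0.537 / 0.552 SD.

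**Step 4: simulation check.** This used 100 participants, exercise balanced within arm, an assumed 30% at the second site, and 20,000 replicates per setting (Monte Carlo SE about 0.3 points). The fixed-baseline model had 84.9 / 83.3 / 81.0% power and the named model 79 to 80%, so the gain is about 1 to 6 points.

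**Step 5: compare with the screened model.** Suppose baseline walk is the only candidate and both triggers are set at 5% (an assumption). In a separate run it entered in 97.5 / 88.2 / 60.2% of trials. Power under the rule was 84.9 / 83.1 / 80.5%, within about half a point of the fixed model. With a 1% trigger and rho 0.9 the rule gave 79.9%, about 1 point below.

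**Step 6: type I error.** Under the null with 5% triggers, following the rule gave 5.0 to 5.3%.

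**Step 7: size of a chance imbalance.** A baseline difference of one standard error (0.2 SD of walk) shifts the named model's estimate by (1 − rho) × 0.2 / √(2(1 − rho)) = 0.077 / 0.063 / 0.045 SD of change. At 40/0.70 m per SD this is 4.4 / 3.6 / 2.6 m; at 40/0.78 it is 4.0 / 3.2 / 2.3 m. The shift is conditional on that imbalance and averages to zero over randomizations.

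**The case against.** The strongest reply is that the plan already deals with baseline walk. It is on the candidate list, association with change alone is enough to bring it in, and step 5 shows that it usually would come in. If the screened result is the one reported, fixing baseline adds almost nothing. That stands, and it bounds the benefit.

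The other branch is that the further adjustment is supportive, which is the more natural reading of text that adds to a model already named. The primary result is then fixed and valid, but it forgoes the precision. That stands too, and it is the branch on which the 1 to 6 points apply.

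Three stronger readings are tempting, and the documents do not support them.

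- **Inflated type I error.** A reader might infer this from the missing cut-offs. Reporting the more favourable of the named and screened results gave 6.1 to 7.2% in simulation, but nothing in the plan provides for such a choice, and a rule applied as written stays near 5%.
- **A power cost from screening many factors.** This appears only if the other factors are unrelated to outcome, whereas section 11.2 calls them prognostic. If they explained 30% of residual variance (assumed, rho 0.8), two simulation runs gave the 5% rule 86 to 88% power against 81 to 84% for fixed baseline alone. The sign reverses, so no general loss can be claimed.
- **Adjustment for on-treatment medication.** Of the baseline, monthly and follow-up visits, section 9.2 says "We will systematically record names and doses of medications and inquire about medication changes at each of these visits", and its adjustment rule is not limited to baseline use. But section 11.2 lists medication use among the screened factors and confines further adjustment to baseline factors. The timing needs stating; a plan to adjust for post-randomization use is not shown.

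**Conclusion.** The point holds as a free improvement. The named primary ANCOVA leaves out a covariate that is already measured and very probably informative. Including it unconditionally is worth about 1 to 6 power points at 0.566 SD with 50 per arm, or under 1 point against a screened model with 5% triggers. The size depends on the assumed rho of 0.9 to 0.7 and on equal variances; the omission itself is plain from the text.

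The stated power is right, and the named model is valid under randomization. The missing cut-offs, the unstated rank of the adjusted model and the undated medication variables are gaps in detail, worth closing in the same edit.

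**What to change.** **Main change.** In section 11.2, make baseline six-minute walk an unconditional covariate, with site and exercise assignment, in the single primary ANCOVA. Use the matching baseline value for each Secondary Aim 3 outcome.

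**Clarifications in the same edit.**

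- Replace the imbalance and association screen for the primary model with a covariate set listed in advance. Any other baseline factor believed to be strongly prognostic should be on that list, because dropping the screen could otherwise lose precision.
- Label every further-adjusted model, including the medication adjustment in section 9.2, as supportive, so that it does not replace the primary result.
- Restrict medication covariates in the efficacy model to baseline use.

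**Cost.** SAP wording before unblinding, one degree of freedom for baseline walk plus one for each further parameter listed, and no new data.

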Randomization. Participants will be randomized to one of four arms using a SAS computer program. Block randomization will be implemented to ensure balance between the four groups throughout recruitment. Block sizes will be randomly selected from eight and twelve. Randomization will be stratified according to whether or not the participant will have a muscle biopsy at baseline. Randomization was stratified by site (added on 1/27/2021 to reflect that when a new site was added, randomization was stratified by site).

Participants who are in the supervised exercise group will attend sessions three times weekly for six months, and participants that are in the “no exercise” group will attend one hour educational sessions once a week for six months. Participants randomized to telmisartan (Group A and Group B) will take 40 to 80 mgs of telmisartan per day. Participants randomized to placebo (Groups C and D) will take placebo daily.

Telmisartan/placebo and assessments. Participants randomized to receive telmisartan will begin at a dose of 20 mgs or 40 mgs daily based on the results of post-run-in assessments. The dose will be increased as tolerated to 80 mgs daily based on results of dose-increase visits and monthly

PROTOCOL TITLE: Telmisartan Plus Exercise to Improve Functioning in PAD: The TELEX Trial

assessments post-randomization. Using results of these assessments, the pharmacy will receive a drug order specifying whether the dose should be changed in order to maintain blinding. The telmisartan dose may be reduced or discontinued and/or replaced with placebo pills. Participants randomized to receive placebo will also return for dose-increase visits and monthly assessments to maintain blinding. All participants will have their blood pressure checked at least monthly and their potassium levels checked at 2- and 5-month follow-up. Patients with a baseline eGFR < 30 will have their potassium level checked at the one-month follow-up visit as well.

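### Randomisation is stratified by planned biopsy and by site, but the default walking, treadmill and questionnaire models carry only site; adding the biopsy stratum is a minor and almost free improvement.

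*Combined protocol and SAP*

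**What the plan says.** Section 9.1 (Randomization) gives two stratification factors. The first is biopsy: "Randomization will be stratified according to whether or not the participant will have a muscle biopsy at baseline". The second is site; a note dated 1/27/2021 records that "when a new site was added, randomization was stratified by site". Blocks are of size 8 or 12 across four arms.

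Section 11.2 (Statistical Analyses) carries one of these two factors into the default models:

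- **Primary ANCOVA (A+B against C+D):** "adjusting for study site (Northwestern or Tulane) and randomization to exercise status". Secondary Aim 3 (treadmill distance, WIQ, SF-36) uses the same two covariates.
- **Pairwise t-tests of six-minute walk (Secondary Aims 1 and 2):** the list of comparisons ends "between Groups A and C, and between Groups B and D, all stratified by study site". The pairwise t-tests in Tertiary Aims 1 and 2 are also stratified by site.
- **Conditional adjustment:** if there is major imbalance, or if "baseline variables are associated with the change in outcome of interest, we will perform ANCOVA to further adjust for the relevant baseline factors". The fixed part of that model is again exercise and site: the extra factors come "in addition to randomization to exercise status and site, for two-group comparison".

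Biopsy status appears in none of these. The examples listed under the conditional clause are open-ended, so biopsy could enter there, but it is not named and no threshold is given.

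**The concern.** An analysis normally includes the factors by which the trial randomised. Blocking within strata balances those factors across arms, so the treatment estimate already varies less than it would under simple randomisation. A model that leaves out a prognostic stratum keeps that stratum's variance in the residual. Its standard error is then too large for the estimate it accompanies, and the test is conservative.

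This plan adjusts for one stratification factor and omits the other without giving a reason. The omitted one is not randomly assigned. Biopsy is optional (section 9.1), closed to participants on anticoagulants (section 9.3), and may not be offered at Ochsner or Tulane (section 6.0). That does not show that biopsy status predicts change in walking, and the documents are silent on the question. What is at stake is a little precision, and whether a stratification factor enters by rule or by a choice made after seeing the data.

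**Working it through.** **1. The plan's own figure.** Section 11.2 gives 50 completers per group, a difference of 0.566 SD, two-sided alpha 0.05 and 80% power. The noncentrality is 0.566/√(2/50) = 2.83. With 98 df, the noncentral t gives 80.0%. The rest of the power table also reproduces with 10% dropout: 81.7, 83.0 and 85.4% for 116, 120 and 128 participants, against the stated 82, 83 and 85%.

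**2. Simple formula for the fix.** Let R² be the share of the variance of change explained by biopsy status. Adding the stratum gives noncentrality 2.83/√(1 − R²) and takes df from 96 to 95. Power is 79.99, 80.8, 82.0 and 84.0% at R² of 0, 2, 5 and 10%. For a pairwise comparison (25 per group, 0.72 SD) the noncentrality is 0.72/√(2/25) = 2.55. Power without the stratum is 70.3%; with it, 70.3, 71.1, 72.5 and 74.8%. This formula ignores incomplete blocks, dropout and the overlap of biopsy with site.

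**3. Simulation of the actual design.** 112 participants were randomised in blocks of 8 or 12 within site-by-biopsy strata, and 100 were analysed after random dropout. The target was 0.566 SD, and the model was telmisartan, exercise and site, without or with biopsy. Assumptions not in the documents: R²; 25% of participants at an added site; overall biopsy uptake of 30% or 50%; biopsy either at every site or only at the main site. Ranges run over the four uptake and site combinations.

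| Assumed R² | Model SE, without ÷ with biopsy | Planned SE against true SD of its estimate | Type I, planned model | Power, planned model | Power with biopsy | Change (points) |
|---|---|---|---|---|---|---|
| 0% | 0.999 | −0.3% | 5.0% | 79.8% | 79.7% | −0.1 |
| 2% | 1.006–1.010 | +0.3 to +0.6% | 4.8–4.9% | 79.9–80.2% | 80.5% | +0.3 to +0.6 |
| 5% | 1.017–1.026 | +1.3 to +1.9% | 4.5–4.7% | 80.2–80.8% | 81.7% | +1.0 to +1.5 |
| 10% | 1.037–1.055 | +2.9 to +4.2% | 4.1–4.3% | 80.6–81.8% | 83.7% | +2.0 to +3.1 |

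With the stratum in the model, type I error is 5.0% throughout. The true SD of the estimate falls by at most 0.1, 0.4 and 1.0% at R² of 2, 5 and 10%, because blocking has already balanced biopsy. Most of the gain therefore comes from a standard error that matches the design.

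A separate simulation (6,000 runs per case, 20% at a second site with no biopsies there, 50% biopsy probability at the main site) gave type I error of 4.8, 4.8, 4.8 and 4.4% without the stratum and 4.8, 5.0, 5.0 and 5.1% with it. That agrees within its simulation error.

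**4. Overlap with site.** If 40% of participants are at an added site, biopsy is done only at the main site and overall uptake is 50%, the site term absorbs more. The power gain is then 0.1, 0.4 and 0.9 points at R² of 2, 5 and 10%.

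**5. Pairwise comparisons (B against D, 0.72 SD), simulated.** Power changes by −0.2 points at R² 0, then by +0.2 to 0.6, +1.0 to 1.7 and +2.4 to 3.7.

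**6. How plausible is each R²?** With uptake q, the gap in mean change between biopsy and non-biopsy participants is √(R²/(q(1 − q))) SD. For the two earlier exercise trials, section 11.2 says "these observed differences represented a difference in six-minute walk change of 40 meters between the intervention and control groups" and equates this with 0.70 and 0.78 SD, so 1 SD is 40/0.78 to 40/0.70, or 51–57 m.

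| R² | Gap at q = 50% | Gap at q = 30% |
|---|---|---|
| 2% | 0.28 SD (14–16 m) | 0.31 SD (16–18 m) |
| 5% | 0.45 SD (23–26 m) | 0.49 SD (25–28 m) |
| 10% | 0.63 SD (32–36 m) | 0.69 SD (35–39 m) |

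An R² of 10% needs a gap 1.1 to 1.2 times the trial's own 0.566 SD target (0.63/0.566 and 0.69/0.566). An R² of 5% needs 0.8 to 0.9 times that target. The upper half of the range is demanding.

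**The case against.** The strongest reply is that the plan already has a safeguard. The conditional clause adjusts for baseline variables associated with change, and that is the only situation in which omitting biopsy costs anything. If the clause were applied to biopsy with a screen at p < 0.05 (an assumed threshold), simulation shows it recovering most of the gain, leaving about 0.0 to 0.3 points of power. This stands as far as it goes. But the plan does not commit to screening biopsy, states no threshold, and makes the decision after seeing outcomes.

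Other points have some force:

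- The fix leaves the clause open for age, sex, baseline outcome and the other listed factors, so the final model may still depend on the data. True: the fix takes only the stratification factor out of that choice.
- R², uptake and site split are all assumed. True, which is why ranges are shown and the upper half is flagged as demanding.
- The absence of bias was shown under random dropout, and payment ($100 per biopsy, $25 for follow-up testing) could make completion differ by stratum. This limits the claim, but it argues for adjusting rather than against.
- The additive term turns the site-stratified pairwise t-tests into linear models, and the rank-sum fallback is not covered. Both should be stated in the plan; neither changes the point.

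**Conclusion.** The mismatch is real and minor. The default analyses of walking, treadmill and questionnaire outcomes omit one of the two factors used to stratify randomisation. Under random dropout this causes no bias and no inflation of type I error; the test is slightly conservative if biopsy status is prognostic. Planned power without the stratum stays at 79.8–81.8% across the assumed range. The power available from adding it runs from a loss of about 0.1 point at R² 0 to a gain of about 3 points at R² 10%. It is under 1 point if much of the biopsy information is already carried by site. The direction does not depend on the assumptions; the size rests on R², uptake and site split, none of which the documents give.

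**What to change.** In section 11.2, name planned baseline biopsy (yes/no, taken from the randomisation file) as a fixed covariate beside site and exercise in the primary and Secondary Aim 3 ANCOVAs. In the pairwise secondary and tertiary comparisons of six-minute walk, treadmill distance, WIQ and SF-36, add it as an additive term beside site, and say that these become linear models. Do not cross the strata, with only about 25 completers per group. State whether the strata also enter the rank-sum fallback. Leave the exploratory muscle analyses unchanged, since biopsy status would be nearly constant there.

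The cost is a few sentences, no new data and no change in sample size. Each model loses one degree of freedom: about 0.1 point of power in the primary analysis and 0.2 in a pairwise comparison if biopsy status turns out not to matter.
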